These data from animal models support the hypothesis that hyperoxia after ROSC may worsen outcomes in post-resuscitation patients. However, clinical data are few. Three preliminary retrospective multi-center analyses have been published. Two of these were published by our research team.^{24,25} In a large (n=6326) cohort of patients admitted to one of 120 U.S. ICUs after cardiac arrest, we found that post-ROSC hyperoxia was **common, an independent predictor of in-hospital death, and associated with lower functional independence among survivors.**²⁴ In a secondary analysis using the same ICU database, we found that a linear, **“dose-dependent” relationship exists between supranormal PaO₂ after ROSC and mortality**²⁵ (see *Preliminary Studies* in sections C.3.1 and C.3.2). However, a recent study from the Australian and New Zealand Intensive Care Society (ANZICS) investigators reported somewhat different results.²⁶ Using a retrospective methodology that replicated our initial study, they found that among 12,000 patients admitted to an ICU after cardiac arrest, patients with hyperoxia (defined by our previous methodology as a PaO₂ >300 mmHg) had significantly higher mortality (59% [95%CI 56-61%]) than patients with normoxia (47% [95% CI 45-50%]), but not patients with hypoxia (60% [95% CI 59-61%]). In a multivariable model adjusting for illness severity, hyperoxia had an odds ratio for mortality of 1.2 (95% CI 1.1-1.6). However, when statistical models with a number of additional adjustments were applied, the association with increased mortality was lost. They concluded that hyperoxia has no consistently reproducible independent association with mortality.²⁶ Therefore, **whether hyperoxia is associated with poor outcome in post-resuscitation patients remains unclear.** Given that post-ROSC hyperoxia exposure is extremely common²⁵, this unanswered question represents a **critical knowledge gap** for resuscitation science. Accordingly, this project will generate **new, critically important knowledge about a fundamental element of post-cardiac arrest care.**

[figure not shown]
B. INNOVATION

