Supplemental oxygen administration is considered a cornerstone of effective CPR, and the belief that increased oxygen delivery is beneficial is historically one of the most basic assumptions of resuscitation. In this application, we **challenge the present paradigm** regarding the role of supplemental oxygen in the treatment of cardiac arrest. Supplemental oxygen may be a *drug with important toxicity* after ROSC. Specifically, we propose an **alternative hypothesis** that hyperoxia after ROSC due to excessive supplemental oxygen is associated with harm. Hypotheses that challenge the prevailing thinking are the hypotheses with the greatest capacity to produce results that challenge conventional clinical practice. This project is further innovative in that we aim to **identify a new potential therapeutic target** in post-resuscitation care. **Figure 3** below displays the classical *Chain of Survival* paradigm for the treatment of cardiac arrest victims, with a new final link emphasizing the importance of post-resuscitation care.²⁷ Rather than studying a completely new treatment strategy (e.g. hypothermia), the proposed study will generate new knowledge about a standard component of **supportive care** (i.e. supplemental oxygen

administration) that may be contributing to poor outcomes. This project is further innovative in that we will measure **neuropsychological function** among survivors at 180 days. Historically, cardiac arrest studies have used crude outcome measures.²⁸ For example, the most often used outcome, Cerebral Performance Category (CPC), requires no cognitive testing. The CPC-1 is compatible with cognitive impairment, so the precise nature of residual deficits is largely unknown. *To date, we are only aware of 5 high quality prospective studies of neuropsychological*

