Using Project IMPACT, a database of ICU admissions from 120 U.S. hospitals, we tested the hypothesis that exposure to hyperoxia (defined as a PaO₂ \geq 300 mmHg on the first arterial blood gas recorded in the ICU) was associated with increased in-hospital death among 6326 patients admitted to an ICU after cardiac arrest. We found that the patients with hyperoxia had significantly higher in-hospital mortality (63% [95% CI 60%-66%]) compared to patients with normoxia (45% [95% CI 43%-48%]; proportion difference 18% [95% CI 14%-22%]), and also compared to patients with hypoxia (57% [95% CI 56%-59%]; proportion difference, 6% [95% CI, 3%-9%]). Survival over time appears in **Figure 4**. In a model controlling for potential confounders (e.g., age, preadmission functional status, comorbid conditions, vital signs, and other physiological indices) including sensitivity analyses that adjusted for hospital factors and propensity of hyperoxia exposure, hyperoxia had an odds ratio for death of 1.8 (95% CI, 1.5-2.2).

Among survivors, hyperoxia was associated with a lower proportion of functional independence at discharge compared to patients with normoxia (29% vs. 38%, respectively; proportion difference, 9% [95% CI, 3%-15%]).

Figure 4: In-hospital death between hyperoxia and normoxia groups.

C.3.2. Dose-dependent relationship between supranormal PaO₂ and risk of death after cardiac arrest.

Kilgannon JH, Jones AE, Parrillo JE, Dellinger RP, Milcarek B, Hunter K, Shapiro NI, Trzeciak S.

[figure not shown]
Relationship between supranormal oxygen tension and outcome after resuscitation from cardiac arrest.

Circulation 2011; 123(23):2717-22.

Using the same ICU database, we tested the hypothesis that a linear, dose-dependent relationship exists between post-resuscitation supranormal oxygen tension (highest PaO₂ over the first 24 hours in the ICU) and in-hospital mortality. Among 4459 patients, the median PaO₂ was 231 (IQR 149-349) mmHg. Over ascending ranges of oxygen tension, we found significant linear trends of increasing in-hospital mortality and decreasing survival as functionally independent, $p < 0.0001$ (**Figure 5**). On multivariable analysis, a 100 mmHg increase in PaO₂ was associated with a 24% increase in mortality risk (odds ratio 1.24 [95% CI 1.18-1.31]) (**Figure 6**).

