C.3.7. Neuropsychological deficits among survivors of out-of-hospital cardiac arrest.

[figure not shown]

This NIH-funded (R01HD046442) prospective study determined the nature and severity of residual cognitive deficits for survivors of OHCA. Thirty OHCA patients who recovered alertness within 1-3 days of ROSC but remained confused at one week, and 30 non-OHCA coronary care admissions (matched controls) were administered neuropsychological testing at 90 days in five cognitive domains: memory, executive function, lexical-semantic, visuoperceptual, and psychomotor (**Figure 8**). Subjects fell into two deficit profiles. Two-thirds had only mild memory deficits and borderline psychomotor deficits compared to controls; 40% in this mild group had returned to work. The other one-third of patients had severe impairments in all domains. In the severe group, only as impairment in memory or psychomotor

domains increased did impairments in other domains appear. Follow-up evaluation at one year revealed discouraging little further cognitive improvement over the levels reached at 90 days. Only one additional subject returned to work. In addition, we assessed health-related quality of life (QOL) at one year using the Sickness Impact Profile-68 (SIP-68)⁴⁴, a measure of health-related functional status in rehabilitation medicine, and found that the OHCA patients reported more adverse effects on health than the cardiac control patients due to poorer psychological health and social participation, not due to effects on physical health.

The proposed study will use a similar methodology for neuropsychological testing and functional assessment at 180 days after resuscitation among survivors.

Figure 8: Composite z-scores – mean and standard deviation – for neuropsychological function in five cognitive domains among cardiac controls (CC), all out-of-hospital cardiac arrests (OHCA), and mild and severely impaired OHCA patients separately. Deficits after OHCA were most common and most severe in memory and psychomotor domains.

D.1. RESEARCH DESIGN AND METHODS

D.1.1 Specific Aims

We will test if a protocol for rapid FiO₂ optimization following ROSC from cardiac arrest is associated with:

- *Reduced in vivo oxidative stress during the post-resuscitation phase of therapy (Aim 1)*

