- *Reduced neurological disability at hospital discharge (Aim 2)*
- *Reduced neuropsychological and functional deficits among survivors at 180 days (Aim 3)*

D.1.2. Overview

Design: Prospective protocol implementation study with an observational comparison group [REOX II (intervention component) versus REOX I (observational component)]

Participants: Adult patients resuscitated from cardiac arrest

Enrollment location: Emergency Departments of 6 urban academic medical centers

Intervention: Implementation of a clinical protocol for rapid FiO₂ optimization after ROSC from cardiac arrest.

Primary outcome: Good neurological outcome (defined as Modified Rankin Scale ≤ 3 ⁴⁵ at hospital discharge).

Secondary outcomes: Neuropsychological tests and ability to return to work among survivors at 180 days.

Mechanistic outcomes: Oxidative stress markers (IsoPs/IsoFs) in plasma 0-6 hours after ROSC.

Estimated sample size and study duration: 280 patients (205 from REOX I and 75 from REOX II).

[figure not shown]
D.2. REOX II Study Protocol

Study setting and population: This study is the second phase in a two-phase study. The initial phase, REOX I, was an observational-only study. As in REOX I, REOX II will identify subjects with return of spontaneous circulation (ROSC) after cardiac arrest in 6 hospitals (Cooper University Hospital, Camden, NJ; Hospital of the University of Pennsylvania and Penn-Presbyterian Medical Center, both in Philadelphia, PA; University of Mississippi Medical Center, Jackson, MS; Methodist Hospital, Indianapolis, IN; and Beth Israel Deaconess Medical Center, Boston, MA). The inclusion criteria are: age > 17 years; cardiac arrest; ROSC achieved; comatose (Glasgow Coma Scale motor score < 6) after ROSC; and clinician intent to treat with target temperature management. The exclusion criteria are: presumed etiology of arrest is trauma, hemorrhage or sepsis; resident of a nursing home or other long-term care facility; known or clinically apparent pregnancy; known lack of commitment to aggressive support by next of kin; and any other condition, that, in the opinion of the investigator, would preclude the subject from being a suitable candidate (e.g. end stage chronic illness with no reasonable expectation of survival to hospital discharge).

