Patient identification and recruitment: Each of the participating centers currently has a mechanism in place for real-time notification of study personnel when an OHCA subject arrives in the emergency department (ED) or when a cardiac arrest occurs in-hospital. Each center has previously validated its notification mechanism to ensure that subjects will not be missed and the population of potentially eligible subjects will be consecutive cardiac arrest subjects. Study personnel will assess patient eligibility and will immediately enroll subjects meeting all inclusion and no exclusion criteria.

Informed consent: In line with REOX I (observational-only component), in REOX II we will begin initial collection of cardiac arrest and post-resuscitation data immediately after ROSC. As per the inclusion criteria all subjects will be comatose during the initial post-ROSC period and therefore will not be able to consent themselves for the study intervention (i.e. protocol for rapid FiO₂ optimization after cardiac arrest). Once a subject is identified to have all inclusion and no exclusion criteria, we will approach surrogates (i.e. next of kin or legally authorized representative)

Figure 9 Flow diagram for enrollment

[figure not shown]
within the first four hours after ROSC for written informed consent and HIPAA authorization prior to implementation of the study intervention. If communication with a surrogate within the first four hours after ROSC is not achieved the subject will not be eligible for the study intervention. However, for subjects who are excluded from the study intervention due to lack of informed consent within the first four hours after ROSC, we will approach subjects or surrogates at a later time for written informed consent and HIPAA authorization for participation in the observational only (REOX I) component of the study including (a) use of plasma samples for research purposes (both stored samples obtained at the time of initial resuscitation and new samples); (b) determination of Modified Rankin Scale at hospital discharge; and (c) follow-up visits for neuropsychological testing at 180 days (**Figure 9**).

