Secondary analyses: We will compare proportions of good neurological outcome [defined as a mRS ≤ 3 (based on the preliminary data of our collaborator, [name], University of Pittsburgh)],⁴⁵ between subjects who receive the study intervention (i.e. rapid FiO₂ optimization) vs. those who do not receive the study intervention, using binomial test. Among survivors, we will compare the 180-day neuropsychological measures (composite z-scores for each cognitive domain) between the same two groups using t-test or Mann-Whitney U as appropriate with corrections for multiple comparisons. We will compare the proportions of patients able to return to work between the two groups using binomial test. We will compare plasma IsoPs/IsoFs at each time point between the two groups using t-test or Mann-Whitney U as appropriate with corrections for multiple comparisons.

Sample Size: The sample size calculation in the initial study proposal was based on the primary outcome, mRS at hospital discharge, and we planned to enroll a total of 266 subjects. To ensure adequate power to test the relationships between the above independent variables and cognitive domains, we assumed a medium relationship strength between the six independent variables and each of the five cognitive domains ($R^2 = 0.15$). In order to achieve 80% power and an $\alpha = 0.05$ we would require a minimal of 85 subjects to undergo neuropsychological testing at 180 days. This sample size will be among the largest prospective studies of

neuropsychological outcomes that we are aware of in the literature.^{8,29-32} Assuming a 15% drop out rate for lost to follow up for neuropsychological testing at 180 days we would require 98 subjects to be discharged with a mRS \leq 4. Based on preliminary data from REOX I we expect 35% of patients will be discharged with a mRS \leq 4 and undergo cognitive testing at 180 days. We would therefore require a minimal total sample size of 280 subjects between REOX I and II combined for the multivariable testing. We have enrolled 200 subjects in REOX I to date. We anticipate additional subjects to be enrolled in REOX I and therefore plan for 75 subjects to be enrolled in REOX II to ensure a total sample size of at least 280 subjects.

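### Every outcome comparison of the FiO2 protocol with no protocol is an unadjusted secondary test between non-randomised groups, while the adjusted models contain no group term

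*Combined protocol and SAP*

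**What the plan says.** **Question.** D.1.1 Specific Aims sets out to test whether a protocol for rapid FiO2 "optimization following ROSC from cardiac arrest is associated with" less oxidative stress (Aim 1), less disability at discharge (Aim 2) and fewer deficits at 180 days (Aim 3). D.1.2 Overview describes a "Prospective protocol implementation study with an observational comparison group", REOX II against REOX I, with 75 and 205 patients. Section B (Innovation) also states a hypothesis about exposure itself: that "hyperoxia after ROSC due to excessive supplemental oxygen is associated with harm".

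**Primary outcome.** D.1.2 gives "Good neurological outcome (defined as Modified Rankin Scale" 3 or below at discharge. D.2, Outcome measures, gives disability on the mRS, described as running from 0 to 6. Sample Size refers to discharge mRS as primary without saying whether it is dichotomised.

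**Adjusted analysis.** D.2, Analysis, regresses discharge mRS, and then each of five cognitive domains, on TWA-PaO2. The covariates are Charlson index, downtime over 20 minutes, initial rhythm, arrest location and PaO2/FiO2 below 100 mmHg. The models are repeated with TWA-SaO2.

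**Group comparisons.** Secondary analyses compares mRS ≤3 between treated patients "vs. those who do not receive the study intervention, using binomial test". Return to work is handled the same way. Cognitive z-scores, and isoprostanes/isofurans at each time point, are compared by t-test or Mann-Whitney. The only corrections named are for multiple comparisons.

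**How groups form.** D.2, Informed consent: "If communication with a surrogate within the first four hours after ROSC is not achieved the subject will not be eligible for the study intervention". Such patients may later consent to the observational component. Sample Size reports 200 REOX I patients already enrolled.

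**The concern.** The aims concern the protocol, but the covariate adjustment is spent on a different exposure. TWA-PaO2 varies within each group as well as between them, so its coefficient does not estimate the association with being treated under the protocol. The analyses that do address the protocol are raw differences between patients who mostly entered at different times and who were sorted partly by whether a surrogate could be reached quickly.

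The plan accepts that comorbidity, downtime, rhythm and arrest location predict neurological outcome, and adjusts for them in Analysis. It then leaves them out of the contrasts that answer the aims. Aim 1 rests on a crude difference alone, and half of its planned time points (the 0-hour sample) precede the intervention. If the groups differ in case mix, a difference in outcome could be credited to the protocol, or a real one hidden.

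**Working it through.** **1. Does any adjusted model contain group?** Sample Size speaks of six independent variables, R² = 0.15, 80% power and α = 0.05, and needs 85 tested. For the overall F test, f² = 0.15/0.85 = 0.1765 and the noncentrality is f²·N:

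- 6 predictors: N = 84, and power at 85 is 80.8%. This reproduces the stated 85 to within one.
- 7 predictors (a group term added): N = 89, and power at 85 is 77.8%.

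The plan's later steps also reproduce: 85 × 1.15 = 98 and 98/0.35 = 280. Six predictors are one exposure plus the five listed covariates. The covariates are introduced as ones to be considered, but the later references to five covariates and six variables close the list. Group is not in it.

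**2. Which outcomes have what analysis?**

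| Outcome | Adjusted model | Group comparison |
|---|---|---|
| mRS at discharge | TWA exposure, mRS as continuous | mRS ≤3, crude, secondary |
| Cognitive z-scores | TWA exposure | crude, secondary |
| Return to work | none | crude, secondary |
| Isoprostanes/isofurans | none | crude, secondary |

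**3. Timing of the 0-hour marker.** Consent must precede the intervention (Informed consent). The 0-hour sample may be left-over clinical plasma drawn immediately after ROSC (Data collection). A 0-hour group difference is therefore a baseline difference.

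**4. Overlap in calendar time.** 200/205 = 97.6% of the planned comparators were enrolled before the 75 intervention patients.

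**5. Power of the crude group test.** The plan gives none. For 205 v 75 and gain d, power ≈ Φ[(d − 1.96·s₀)/s₁], where s₀ is the pooled and s₁ the unpooled standard error. The mRS ≤3 rate in REOX I is not given, so 20% to 35% is assumed:

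- Comparator 20%: 80% power at d = 16.6 points; 43% power for 10 points.
- Comparator 35%: 80% power at d = 18.6 points; 34% power for 10 points.

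**6. Illustration of what case mix could do (arbitrary assumptions).** Suppose good outcome is 50% after a shockable and 15% after a non-shockable rhythm, with 40% shockable in REOX I, 50% in REOX II, and no protocol effect. Expected rates are 0.4 × 50 + 0.6 × 15 = 29.0% and 0.5 × 50 + 0.5 × 15 = 32.5%. The spurious difference is 3.5 points. With s₀ = 0.0618 and s₁ = 0.0627, the two-sided 5% test rejects about 9% of the time. A separate simulation, with an assumed 10-point imbalance in rhythm and downtime and no effect, gave a spurious difference of about 5 points and 14% type I error unadjusted, against about 0 points and 5% adjusted. These show the mechanism and that adjustment removes measured imbalance. They do not estimate bias in this study.

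**7. Can the data carry adjustment?** Group, four baseline covariates and age make six terms.

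- mRS ≤3: at an assumed 20% to 35% of 280, there are 56 to 98 events, or 9 to 16 per term.
- Cognition: six terms need N = 84 by the plan's own method, within the 85. Adding five site indicators makes 11 terms and needs N = 106; power at 85 falls to 67%.
- Return to work: if the roughly 25% reported for the earlier survivor cohort applied (assumed), 85 × 0.25 ≈ 21 events, or 3.5 per term.

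**The case against.** The strongest reply is that the lead analysis is deliberately the exposure model, which answers the hypothesis in section B and is adjusted, and that the group contrasts are labelled secondary and the aims claim only association. The first part stands: the plan does have adjusted analyses, and they bear on hyperoxia. But they do not estimate the association with the protocol, and for Aim 1 there is nothing else.

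Four stronger readings are tempting and are not supported.

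- *The confounding is large, as the cited cohorts show.* Section A.3 reports that "when statistical models with a number of additional adjustments were applied, the association with increased mortality was lost", and C.3.1 reports an odds ratio of 1.8 "In a model controlling for potential confounders (e.g., age, preadmission functional status, comorbid conditions, vital signs" among others, against a crude (0.63/0.37)/(0.45/0.55) = 2.08. These are mortality contrasts of hyperoxia with normoxia, not of these two groups. In the A.3 cohort the crude odds ratio is (0.59/0.41)/(0.47/0.53) = 1.62 and the severity-adjusted interval is 1.1 to 1.6. Taking normoxia as the reference, adjustment removed anywhere from 3% (1 − ln 1.6/ln 1.62) to 80% (1 − ln 1.1/ln 1.62) of the log odds ratio. Nothing about size carries over.
- *Every comparison of the groups is affected.* The monitoring board's 15% rule for serious adverse events also compares the groups crudely, but it is a safety threshold. The point concerns outcome comparisons.
- *The plan consistently makes scale mRS primary apart from D.1.2.* Only Outcome measures says so explicitly. Analysis never uses the word primary, and Sample Size leaves the form open.
- *Adjustment would make the contrast causal.* It would not. In simulation, an assumed unmeasured imbalance left 2.2 to 2.7 points of bias with or without adjustment.

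**Conclusion.** The point holds, and should be fixed. All outcome comparisons of protocol with no protocol are unadjusted and secondary, the adjusted models have no group term, and the Aim 1 markers and return to work have no adjusted analysis. This follows from the text alone. The analyses of the protocol can be located; the fault is that they are crude, and that the outcome D.1.2 calls primary is analysed only as secondary.

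The direction and size of any confounding are unknown. The power figures in steps 5 and 7 rest on the assumed 20% to 35% comparator rate, and the imbalance scenarios in step 6 are arbitrary.

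**What to change.** 1. **mRS ≤3.** In Secondary analyses, make the main group analysis a prespecified logistic regression on group, adjusted for Charlson index, downtime over 20 minutes, rhythm, arrest location and age. Include PaO2/FiO2 below 100 only if taken from the 0-hour blood gas, and leave out TWA-PaO2, which lies downstream of the intervention. Handle site by a random intercept or penalisation. Report a standardised risk difference with a bootstrap 95% interval, and keep the crude test as descriptive.
2. **Aim 1.** Compare 6-hour isoprostanes/isofurans by linear model on group, with the 0-hour value and the same covariates. Report 0-hour levels as baseline only.
3. **180-day outcomes.** For cognitive z-scores use group, the four baseline covariates and age, without site indicators. For return to work use a penalised model with the same covariates.
4. **Consistency.** Make D.1.2, Outcome measures, Analysis, Secondary analyses and Sample Size agree on one primary outcome and one primary analysis. Name the adjusted group models as the analyses of Aims 1 to 3. If the group comparison becomes primary, state its detectable gain (about 17 to 19 points under the assumed rates).
5. **Limitation.** State unmeasured and calendar-time confounding for every group contrast.

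**Cost.** This is SAP wording and a few models. Four of the covariates are already in the plan, and age falls within the baseline demographics it collects. The downsides are a few more terms, thin events at the low end, and residual confounding. In simulation without imbalance, the adjusted Wald test had type I error of 5.6% to 6.5% against 4.6% to 5.5% unadjusted, which is why a bootstrap interval is preferred; standard errors were 6% to 8% smaller.
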